## Rationale

Skeletal muscle is a highly plastic tissue, capable of adapting to changes in nutritional intake and contractile activity. For instance, resistance exercise results in a mild stimulation of rates of muscle protein breakdown (MPB) but a greater stimulation of the rates of muscle protein synthesis (MPS) (1-3). When resistance exercise is performed prior to protein ingestion there is a synergistic combination of the two stimuli such that rates of MPS are stimulated over and above those of MPB (4-6). Thus, repeated bouts of resistance exercise, when coupled with protein ingestion, result in the accretion of skeletal muscle protein referred to as hypertrophy (7). Importantly, by changing the nature of the exercise stimulus, it is possible to redirect the focus of the type of skeletal muscle proteins that are being synthesised. For example, we know that prolonged and repeated lower-load dynamic stimulation of skeletal muscle (*i.e.*, endurance exercise training) results in an increase in the expression of mitochondrial genes (8), proteins (8-10), and ultimately enhanced mitochondrial content (11), leading to a shift towards an oxidative phenotype, and improved fatigue resistance (12). Resistance exercise training also stimulates the transcription of genes and accrual of new muscle proteins (13, 14), but these genes and proteins are largely associated with the myofibrillar protein fraction, and regular resistance exercise leads to muscle hypertrophy and increased force-generating capacity (15, 16). However, during the early stages of exercise training, particularly in training-naïve participants there is a significant increase in the expression of genes common to both modalities of exercise (17, 18). It is only with sustained exercise training that there is a ‘fine tuning’ of the transcriptome, the protein synthetic response, and then the proteome that gives rise to divergent hypertrophic and oxidative phenotypes (17, 19).

## Transcriptional responses to exercise training

Increases in mRNA expression following each exercise session result in enhanced translation of proteins, and ultimately adaptive changes in muscle protein content (12, 19). The temporal pattern of these changes with respect to endurance and resistance exercise training is now becoming clearer. Exercise-induced mitochondrial biogenesis, for example, is a characteristic feature of endurance exercise training (9, 12, 20) and is underpinned by the coordinated up-regulation of both mitochondrial and nuclear transcripts that encode for proteins involved in the electron transport chain (21-23), and lipid metabolism (24). These transcripts include peroxisome proliferator-activated receptor gamma co-activator (PGC)-1 $\alpha$ , nuclear respiratory factors (NRFs), and the mitochondrial transcription factor A (TFAM)(25-27). An acute bout of endurance exercise activates sensors of cellular stress (8, 28), decreases methylation of promoter regions (29), stimulates phosphorylation of mediators of translation initiation (16), and increases the expression of the aforementioned transcripts (PGC-1 $\alpha$ , NRFs, TFAM) (8, 12). The transient increase in the expression of genes in the hours following an acute endurance exercise session provides the gene template that precedes the respective increases in protein content observed during exercise training (8, 9). Compared to our understanding of transcriptional responses to endurance training, the corresponding picture with

respect to resistance exercise is relatively less complete. Resistance exercise results in the phosphorylation (i.e., activation) of the mechanistic target of rapamycin complex 1 (mTORC1)(30-33). mTORC1 activation serves to enhance MPS by (1) activating downstream protein kinases such as the ribosomal protein of 70 kDa S6 kinase 1 (p70S6K1) and 4E-binding protein-1 (4EBP1), which subsequently promote ribosomal binding to mRNA to initiate protein synthesis (34-37) and (2) up-regulating the transcription of the translational machinery itself (mRNA, ribosomal content) (38). Thus, resistance exercise stimulates an increase in mTORC1 activity and promotes increases in the rates of myofibrillar MPS through both increased translational efficiency (protein synthesized per unit of mRNA) and translational capacity (the abundance of the translational machinery; ribosomes) (31, 33).

### **Posttranslational modification of proteins**

Key to exercise-induced adaptation is post-translational modification of proteins. One important post-translational modification is known as phosphorylation. Phosphorylation is the addition of a phosphate group to a target protein by a protein kinase using ATP and Mg (39). The addition of this phosphate can promote the catalytic activity or binding status of a protein resulting in a biological downstream effect. There are over 500 kinases in the human 'kinome'. We (39, 40) and others (16) often assess the phosphorylation status of single or multiple (~ten) kinases/proteins in response to exercise to gain a mechanistic understanding of how exercise alters the skeletal muscle phenotype. However, current methods are largely semi-quantitative (Western blotting) and are biased in terms of which proteins are studied (i.e., the experimenter can only select a limited number of kinases/proteins to measure). Our understanding of how skeletal muscle adaptation is influenced by phosphorylation is therefore limited. Recent developments in mass spectrometry (41, 42) have enabled a wider interrogation of the phosphorylation status of proteins in response to exercise. Indeed, one study, using advanced liquid chromatography-mass spectrometry, revealed 1,004 unique exercise-regulated phosphorylation sites on 562 proteins in human skeletal muscle biopsy samples obtained before and after a bout of endurance exercise (41). This seminal finding has significantly advanced our knowledge regarding how endurance exercise impacts phosphorylation. Yet, no measurements of end-point MPS were made. Moreover, comparable work has not been performed with resistance exercise. The aim of our investigation is to conduct a similar global phosphoproteomic analysis of skeletal muscle using advanced mass spectrometry following both endurance and resistance exercise in humans. We will also directly measure rates of MPS for the 3 hours following exercise.

The aim of our investigation is to conduct a similar global phosphoproteomic analysis of skeletal muscle using advanced mass spectrometry following resistance and aerobic exercise in humans.

## Specific Objectives

1. Our primary objective is to examine the effect of resistance exercise on the human skeletal muscle phosphoproteome.
2. Our secondary objective is to assess changes in rates of myofibrillar and mitochondrial MPS following resistance and endurance exercise.

## Hypotheses

We hypothesize that:

1. Both resistance exercise and endurance exercise will result in the widespread phosphorylation of proteins involved in the regulation of energy metabolism, transcription, translation and muscle protein synthesis.
2. Resistance exercise will increase myofibrillar MPS to a greater extent than endurance exercise.
3. Endurance exercise will increase rates of mitochondrial MPS to a greater extent than resistance exercise.

## Participants

### ***Inclusion Criteria***

In order to participate in this study, participants must be male between the ages of 18 and 30 years and have performed resistance exercise 3 times per week for at least 1 year.

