## **Recruitment**

Twelve participants (6 male: 6 female) participants will be recruited for this study through poster advertisements. Potential participants will be asked if they meet all of the inclusion criteria and none of the exclusion criteria. During an initial screening visit those who qualify and are interested in participating will be invited to the Exercise Metabolism Research Group (EMRG) laboratory, Ivor Wynne Centre (IWC) at McMaster University to begin testing for the study. The potential participants will then be required to read the Information and Consent Form. A written copy of the consent form will be provided for the participants to read by themselves. Written informed consent will then be obtained.

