## **Sample Size**

This study is an observational pilot investigation. Previous work has detected changes in our primary outcome (phosphoproteome) following endurance exercise with only 4 male participants (41). For the current study, we wish to recruit both male and female participants. Therefore - accounting for participant attrition - we will aim to recruit 12 participants.

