## **Methodology**

A schematic illustration of the experimental design and experimental trial can be seen in Figures 1 and 2, respectively. In a within-subject repeated measures cross-over design, 12 participants (6 male and 6 female) will attend the laboratories at the Dept. of Kinesiology on 6 separate occasions. On the first occasions participants will be assessed for body composition using dual-energy x-ray absorptiometry (DXA) after an overnight fast (~10 hours) followed by familiarization on resistance exercise and endurance exercise equipment. At this point, your two legs will be randomly assigned to the resistance exercise or endurance exercise group.

On the second visit, participants will perform a 1-repetition maximum test on a leg press and leg extension machine. These tests will be used to determine the workload performed on the experimental trials. On the third visit participants will perform a  $V_{02\text{ max}}$  test on a cycle ergometer to determine their aerobic fitness. On the same day, subjects will be familiarized with single-leg cycling. On visit 4, subjects will perform another  $V_{02\text{ max}}$  test on a cycle ergometer using one leg only. This test will determine the intensity of cycling performed on the experimental trial. To ensure the intensity is appropriate, the subjects will be familiarized with the experimental trial training programs (see “Exercise protocols” below).

Subjects will then embark on a 3-day period of controlled diet and exercise followed by experimental trials (visits 5 and 6) separated by 1 week. The reason for the two independent trials is that the measurement of MPS requires the

infusion of a stable amino acid isotope (L-[*ring*-C6] phenylalanine), which interferes with the assessment of the phosphoproteome due to the fact they both detect changes in protein mass. Thus the first trial will be conducted to assess exercise-induced changes in the phosphoproteome and the second for MPS, using the L-[*ring*-C6] phenylalanine isotope.

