### Skeletal Muscle Biopsies and Analyses:

During the study, 7 muscle biopsies will be collected (days -3, 0 [4 biopsies], 1, and 2). This procedure involves the removal of a small piece of muscle tissue using a sterile hollow needle from the quadriceps muscle (*vastus lateralis*) under local aesthetic (lidocaine). A small piece of muscle (~100 mg) will be

collected at each time point. Following the biopsies, the incisions will be closed with instant medical adhesive, and wrapped with a tensor bandage. Phosphoproteomic analysis will be conducted by mass-spectrometry as previously described (41). Myofibrillar MPS will be calculated using the precursor-product equation: myofibrillar MPS =  $([E_{2b}-E_{1b}]/[E_{ic} \times t]) \times 100$ .  $E_b$  represents the enrichment of bound myofibrillar protein,  $E_{ic}$  is the average intracellular enrichment between two biopsies, and  $t$  is the tracer incorporation time in h. As we will employ 'tracer naïve' participants (had not previously participated in a study protocol where L-[*ring*-C6] phenylalanine was infused), a pre-infusion blood sample will be used for the calculation of resting myofibrillar MPS (50). Myofibrillar and intracellular enrichments of L-[*ring*-C6] phenylalanine will be measured as previously described (51). Integrated (i.e., days) rates of muscle protein synthesis (MPS) will be determined using the D2O method. Briefly, H enrichment of saliva (precursor) and muscle (product) pools (relative to H) will be determined using isotope ratio mass spectrometry and myofibrillar fractional synthetic rate determined, as previously described (52, 53).

Diets:

*Ad libitum* 3-day dietary records for each participant will be collected and analyzed for baseline macronutrient intake. During the study, all food will be provided to the participants as frozen meals (Supplier: Copper County Foods), and pre-weighed and measured snack items.

Physical activity:

Recreationally active young men (assessed through physical activity questionnaire) will be recruited. Participants will be asked to maintain their habitual activity for the duration of the study.

Exercise Protocol:

Resistance exercise: 5 sets × 10 reps 75% 1RM leg press followed by leg extension, with 2 min recovery between sets and exercises (50).

Endurance exercise: 4 × 5 min @ 65% single leg peak power with 2.5 min recovery @ 20% peak power (MacInnis 2016)

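### The inclusion criterion admits men only, yet the plan is to enrol 6 men and 6 women, so half of the 12 planned participants are ineligible as written

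*Combined protocol and SAP*

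**What the plan says.** Two places in the combined protocol and SAP restrict the study to men:

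- Inclusion Criteria: "participants must be male between the ages of 18 and 30 years and have performed resistance exercise 3 times per week".
- The Physical activity paragraph, under Skeletal Muscle Biopsies and Analyses: "Recreationally active young men (assessed through physical activity questionnaire) will be recruited".

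Three places plan for both sexes:

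- Recruitment: "Twelve participants (6 male: 6 female) participants will be recruited".
- Sample Size: "For the current study, we wish to recruit both male and female participants". The next sentence draws the number from this: "Therefore - accounting for participant attrition - we will aim to recruit 12 participants".
- Methodology: "12 participants (6 male and 6 female) will attend the laboratories".

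The Recruitment section then ties enrolment to the criteria: "Potential participants will be asked if they meet all of the inclusion criteria and none of the exclusion criteria".

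**The concern.** The eligibility rule and the enrolment plan cannot both be followed. The inclusion criterion is the rule that screening staff apply, and it rejects every woman. The enrolment plan needs women for half its places.

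Three things are at stake. The first is conduct: one instruction has to be broken, and once enrolment has begun a breach can only be recorded as a deviation. The second is generalisability: the document does not settle whether the findings are meant for young men or for young adults of both sexes. The third is the basis for the sample size: including both sexes is part of the short argument for 12, and that part disappears if the study is for men only.

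**Working it through.** **Inputs.** Sex criterion: male (Inclusion Criteria). Planned total: 12 (Recruitment, Sample Size, Methodology). Planned split: 6 men and 6 women (Recruitment, Methodology). Screening rule: all inclusion criteria must be met (Recruitment).

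**The plan's own figure.** 6 + 6 = 12, so the split agrees with the total and the three sections agree with each other. The number 12 cannot be re-derived as a sample-size calculation, because the document gives no significance level, power, effect size, variability or attrition rate. It cites earlier work that detected changes with 4 men. Purely as illustration, 4 per sex gives 4 × 2 = 8. Reaching 12 from 8 through attrition d requires 8/(1 − d) = 12, so d = 1 − 8/12 = 33%. The document states no such rate.

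**Share ineligible as written.** Planned women / planned total = 6/12 = 50%.

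**Enrolment under each way of following the text.**

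| Reading | Men | Women | Consequence |
|---|---|---|---|
| Male-only criterion and 6:6 split both enforced | 6 | 0 | 6 of 12 places filled |
| Male-only criterion, all places given to men | 12 | 0 | Split and both-sexes reason for 12 not met |
| 6:6 enrolled | 6 | 6 | 6/12 = 50% eligibility deviations |

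None of the three satisfies every section.

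**Could the text be read as consistent?** The word male cannot be taken as generic, because Recruitment, Sample Size and Methodology each set it against female. No section of the available text exempts women from the criterion. All five places are current operative text, not a record of changes.

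**Effect on the comparisons.** The Methodology describes a within-subject crossover in which "your two legs will be randomly assigned to the resistance exercise or endurance exercise group". Sex is constant within a participant, so the sex mix does not by itself bias a comparison between that participant's legs. No objective or hypothesis concerns sex. The available text has no statistical analysis section, so any further effect on the analysis cannot be judged.

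**The case against.** The strongest reply is that the intention is plain. Three sections agree on both sexes, two of them with an exact split, so the male-only wording looks like a remnant that any reader would correct. The study is described as an observational pilot, has no objective about sex, and suffers no demonstrated bias or power error. On that view this is an editorial slip.

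Much of this is fair. Remnant wording is the likelier explanation, but it remains an inference. The male-only restriction appears in two separate sections, one of which is the controlling eligibility rule, and the VO2peak section also uses masculine pronouns in its test criteria. Reference 43, on eumenorrheic females, is the only one of the 53 listed references not cited in the available text. That could reflect text on women added or text on women removed, so it does not settle the matter.

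A clear intention would not cure the problem in any case. The rule as written still excludes half the planned sample, and screening staff are told to apply it in full. What does stand is the limit on the consequences: neither bias in the leg comparisons nor a wrong power figure has been shown.

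**Conclusion.** The concern holds. The male-only criterion contradicts the planned enrolment, and 6 of 12 planned participants (50%) are ineligible as written. This should be corrected before enrolment, because it decides who may enter the study.

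The conclusion rests on the stated split and on the screening rule being applied literally. It does not depend on which population the sponsor intends. The effect shown is on eligibility, generalisability and, if men only are intended, the stated reason for 12.

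**What to change.** The sponsor should state which population is intended and make all sections agree.

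- **If both sexes are intended**, which three sections support: in the Inclusion Criteria, change male to male or female, and in the Physical activity paragraph, change young men to young men and women. The 6:6 target can stay in Recruitment and Methodology. Make the pronouns in the VO2peak section neutral, and check that the remaining inclusion criteria and the 7 exclusion items suit both sexes. The cost is a few words, plus any edits that this check brings up.
- **If men only are intended**: change Recruitment and Methodology to men only, delete the both-sexes sentence in Sample Size, and restate why 12 are needed. This costs more, because the number itself may need review.

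The allocation of legs is unaffected under either option.

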### ***Exclusion Criteria***

Participants cannot participate in, or will be released from, this study if they meet one of more of the following criteria:

- Smoker or user of tobacco products
- High physical activity.
- Have health problems such as: renal or gastrointestinal disorders, metabolic disease, heart disease, vascular disease, rheumatoid arthritis, diabetes, poor lung function, uncontrolled blood pressure, dizziness, thyroid problems, or any other health conditions for which you are being treated that might put you at risk for this study.
- Taking anti-diabetic, anti-inflammatory, platelet inhibitor, or anti-coagulant medications.
- Use of an investigational drug product within the last 30 days.
- Have participated in an infusion protocol in the last year.
- Do not understand English or have a condition the PI believes would interfere with a participants' ability to provide informed consent, comply with

the study protocol, or which might confound the interpretation of the study results or put someone at undue risk.

## **Recruitment**

Twelve participants (6 male: 6 female) participants will be recruited for this study through poster advertisements. Potential participants will be asked if they meet all of the inclusion criteria and none of the exclusion criteria. During an initial screening visit those who qualify and are interested in participating will be invited to the Exercise Metabolism Research Group (EMRG) laboratory, Ivor Wynne Centre (IWC) at McMaster University to begin testing for the study. The potential participants will then be required to read the Information and Consent Form. A written copy of the consent form will be provided for the participants to read by themselves. Written informed consent will then be obtained.

## **Sample Size**

This study is an observational pilot investigation. Previous work has detected changes in our primary outcome (phosphoproteome) following endurance exercise with only 4 male participants (41). For the current study, we wish to recruit both male and female participants. Therefore - accounting for participant attrition - we will aim to recruit 12 participants.

## **Methodology**

A schematic illustration of the experimental design and experimental trial can be seen in Figures 1 and 2, respectively. In a within-subject repeated measures cross-over design, 12 participants (6 male and 6 female) will attend the laboratories at the Dept. of Kinesiology on 6 separate occasions. On the first occasions participants will be assessed for body composition using dual-energy x-ray absorptiometry (DXA) after an overnight fast (~10 hours) followed by familiarization on resistance exercise and endurance exercise equipment. At this point, your two legs will be randomly assigned to the resistance exercise or endurance exercise group.

On the second visit, participants will perform a 1-repetition maximum test on a leg press and leg extension machine. These tests will be used to determine the workload performed on the experimental trials. On the third visit participants will perform a  $V_{02\text{ max}}$  test on a cycle ergometer to determine their aerobic fitness. On the same day, subjects will be familiarized with single-leg cycling. On visit 4, subjects will perform another  $V_{02\text{ max}}$  test on a cycle ergometer using one leg only. This test will determine the intensity of cycling performed on the experimental trial. To ensure the intensity is appropriate, the subjects will be familiarized with the experimental trial training programs (see “Exercise protocols” below).

Subjects will then embark on a 3-day period of controlled diet and exercise followed by experimental trials (visits 5 and 6) separated by 1 week. The reason for the two independent trials is that the measurement of MPS requires the

infusion of a stable amino acid isotope (L-[*ring*-C6] phenylalanine), which interferes with the assessment of the phosphoproteome due to the fact they both detect changes in protein mass. Thus the first trial will be conducted to assess exercise-induced changes in the phosphoproteome and the second for MPS, using the L-[*ring*-C6] phenylalanine isotope.

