#### Acute protocols (Visits 5 + 6)

On visit 5 participants will arrive at the laboratory at approximately 0640 after a 10h overnight fast. After a brief assessment, subjects will rest on a bed for 3 hours. After this period, a skeletal muscle biopsy will be obtained and participants will perform a bout of resistance exercise with a randomised leg, followed by a bout of endurance exercise. Skeletal muscle biopsies will again be obtained immediately following both bouts of exercise and again 3h following exercise. On visit 6, participants will again arrive at the laboratory at approximately 0640 after an overnight fast. This time, a catheter will be placed in the upper forearm. After the placement of the catheter, a primed constant infusion of L-[*ring*-C6] phenylalanine will be commenced to measure rates of MPS and a catheter placed in the contralateral arm for repeated blood sampling. Exercise and skeletal muscle biopsies will be obtained as in visit 5 (see Figure 2). We have routinely obtained ethical approval and published papers for studies that employ skeletal muscle biopsies and stable amino acid tracers in human volunteers (3, 14, 44-49). [name], a licenced physician, has approved our standard operating procedure and will oversee all muscle biopsy and catheter infusions.

[figure not shown]
[figure not shown]

Figure 1 Schematic illustration of experimental design.

**R.Ex-** 3 sets  $\times$  10 reps 70% 1RM leg press followed by leg ext.  
2 min recovery between sets and exercises.

**E.Ex-** 4  $\times$  5 min @ 65% single leg peak power  
w/ 2.5 min recovery @ 20% peak power.

\* Timing will change depending on exercise order

Figure 2. Schematic illustration of Visit 6.

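### Legs are randomised with no stated method and no balance for dominance; with 12 people, blocking on dominance would remove avoidable chance imbalance from the resistance–endurance comparisons

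*Combined protocol and SAP*

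**What the plan says.** The Methodology section describes the design thus: "In a within-subject repeated measures cross-over design, 12 participants (6 male and 6 female) will attend" the laboratory. At the first visit, "your two legs will be randomly assigned to the resistance exercise or endurance exercise group". The Acute protocols section adds that, after the rest period, "a skeletal muscle biopsy will be obtained and participants will perform a bout of resistance exercise with a randomised leg", and the endurance bout follows. I read these as one allocation: each person has one resistance leg and one endurance leg.

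Neither section says how the sequence is generated, or whether it is blocked or stratified. Leg dominance is not mentioned anywhere, and the text contains no analysis model.

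Hypotheses 2 and 3 compare resistance with endurance exercise directly, for myofibrillar and mitochondrial protein synthesis. The primary objective is the effect of resistance exercise on the phosphoproteome, which is a pre-post question.

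Two neighbouring passages matter for the remedy:

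- **Sex.** Recruitment plans for "Twelve participants (6 male: 6 female"), but the Inclusion Criteria admit males only.
- **Biopsies.** The Acute protocols section has one resting biopsy with no leg named, and then: "Skeletal muscle biopsies will again be obtained immediately following both bouts of exercise and again 3h following exercise". The section on skeletal muscle biopsies lists seven for the study, four of them on day 0.

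**The concern.** In this design the leg is the randomised unit, and hypotheses 2 and 3 are differences between two legs of the same person. Pairing removes everything the legs share, but not a systematic difference between the dominant and non-dominant leg. If the dominant leg does resistance exercise in most participants, part of any dominance difference is read as an effect of modality.

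In a large trial randomisation makes this negligible. With 12 people it may not. The trial will be run once, the allocation cannot be repaired after the biopsies, and without a dominance term the analysis has no way to separate the two effects.

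**Working it through.** **Inputs.** n = 12 (Methodology, Recruitment). Allocation is random with no method stated. I assume simple 1:1 randomisation; the documents do not say so. The dominance difference d is not given, so results are multiples of d or use assumed values. The plan gives no figure on imbalance to reproduce, and its target of 12 has no power calculation behind it.

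**1. How often the split is uneven.** Let k be the number whose dominant leg does resistance exercise, so k ~ Binomial(12, 0.5) with 2^12 = 4096 equally likely outcomes.

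- Exactly 6:6: 924/4096 = 22.6%.
- 8:4 or worse: 2 × (495 + 220 + 66 + 12 + 1)/4096 = 1588/4096 = 38.8%.
- 9:3 or worse: 2 × (220 + 66 + 12 + 1)/4096 = 598/4096 = 14.6%.
- 10:2 or worse: 2 × (66 + 12 + 1)/4096 = 3.9%.

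**2. What a split does to the contrast.** Write each person's resistance-minus-endurance difference as the true effect, plus d if the dominant leg did resistance or minus d if it did not, plus error. The mean shifts by d(2k − 12)/12.

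- 8:4: 4d/12 = 0.33d.
- 9:3: 6d/12 = 0.50d.
- Over all allocations: expectation 0, SD d/√12 = 0.29d.

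**3. Effect on the paired test.** This was simulated with 100,000 runs, n = 12, no true effect, and an error SD of the paired difference equal to 1.

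| Assumed d | Type I error overall | Given 6:6 | Given 9:3 or worse |
|---|---|---|---|
| 0.5 SD | 5.1% | 2.9% | 11.4% |
| 1 SD | 5.1% | 0.7% | 21.8% |

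The overall rate is right because the unmodelled dominance difference also inflates the estimated SD. The 6:6 column shows that blocking alone makes the unadjusted test conservative. The gain is realised only if dominance is also in the model.

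**4. Precision lost.** With simple allocation and no dominance term, the variance of the mean difference is (1 + d²)/12, against 1/12 when blocked and modelled. The standard error is larger by √(1 + 0.5²) = 1.12 at d = 0.5 SD, and by √(1 + 1²) = 1.41 at d = 1 SD.

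**5. Attrition after blocking 6:6.** Losing two from the same group leaves 6:4, a shift of up to 2d/10 = 0.2d. Losing four leaves 6:2, up to 4d/8 = 0.5d. Both are worst cases, and the shift applies only if dominance is left out of the model.

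**The case against.** The strongest reply is that random assignment already does its job: the expected shift is zero and the test keeps its 5% level overall. That stands. The 0.33d and 0.50d figures describe allocations that may occur by chance, d is unknown and may be small, and the study calls itself an observational pilot. A stable dominance difference also cancels from the primary pre-post contrast when both samples come from the same leg. What remains is a precision argument for hypotheses 2 and 3, made worthwhile because the remedy costs so little.

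A reader might infer three stronger claims. The documents do not support them.

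- **That allocation is unrestricted.** The text says random and no more. A blocked list may exist without being described.
- **That the resting-biopsy leg is not allocated, so the pre-post contrast is biased.** The text does not name the leg, but Figures 1 and 2, to which it refers, were not available in the copy read and may show it. The number of biopsies is itself unsettled. Read as one per exercised leg per time, the Acute protocols section gives 1 + 2 + 2 = 5 per visit and 10 over two visits, against seven in the biopsy section. A fixed choice of resting leg could introduce a systematic effect, but no such choice is documented.
- **That the resting biopsy should be split evenly between the resistance and endurance legs.** This is a trade-off. Assume a correlation with the post-exercise sample of 0.7 in the same leg and 0.5 in the opposite leg. The variance of change is proportional to 1 minus the correlation: 0.3 if rest is always taken from the resistance leg, and (0.3 + 0.5)/2 = 0.4 if split. The SD of the primary resistance contrast rises by √(0.4/0.3) = 1.15, about 15%. Splitting balances any prior-biopsy effect between modalities but leaves half of it in each pre-post contrast. Always using the resistance leg puts all of it into that leg's change and into the resistance–endurance comparison. The documents give no basis for ranking these.

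**Conclusion.** The concern holds as a design improvement for hypotheses 2 and 3. The method of leg allocation is unstated and dominance is not balanced. If allocation is simple, there is about a two-in-five chance of a split of 8:4 or worse and a one-in-seven chance of 9:3 or worse, with the shifts given above. The consequence is chance imbalance and loss of precision, not bias in expectation.

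The probabilities rest on simple randomisation of 12 completers. The practical size rests on d, which the documents do not give: if d is near zero, little is lost either way. The resting-biopsy leg is a matter for clarification, not a demonstrated flaw.

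**What to change.** 1. State the randomisation method. Use a prepared allocation list blocked on leg dominance, so that the dominant leg does resistance exercise in half of the participants. Define dominance and record it before allocation.
2. Block within sex if both sexes are enrolled: with six of each, three and three. The male-only Inclusion Criteria must first be reconciled with Recruitment and Methodology.
3. Write dominance into the analysis as a term in the paired resistance–endurance comparison. If legs have already been allocated, the term alone still removes the shift. The standard error, relative to a 6:6 split, is then multiplied by 1/√(1 − 0.5²) = 1.15 at 9:3, or 1/√(1 − 0.33²) = 1.06 at 8:4.
4. Reconcile the biopsy schedules in the Acute protocols section and the biopsy section, and state the leg of each biopsy in the text. Do not adopt a rule splitting the resting biopsy between modalities on the strength of this point.

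The cost is one list, a few lines of text and one degree of freedom (11 to 10 with 12 completers). No extra participant, visit or biopsy is needed. Attrition can bring back some imbalance, which the model term then handles at some cost in precision.
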